- Significant psychiatric illness or any other condition rendering the subject incapable of understanding the objectives and potential consequences of the study

Participants will be randomly assigned using a computer-generated random sequence at a 1:1 ratio to either the Telemedicine group or the Standard of Care (SoC) group. All participants will be followed for six months, unless they died or if they withdrew consent and decided not to

“Improving Glycemic Control in DM2 Patients in the Ambulatory Setting”

PI [name]
NCT04800471

continue participating in the study. No sample size calculations are provided due to the pilot nature of this study. Instead, we used a convenience sample of 30 subjects. This study was approved by the BVAMC IRB Committee.

Following consent, subjects in both groups will have a baseline research visit where they will be placed on a ("blinded") Dexcom G6 CGM device for ten days to obtain baseline CGM glucose data. A baseline assessment of PA will be obtained by completion of the Senior Fitness test. Subjects will be then randomized to either Telemedicine or the Standard of Care (SoC).

Participants in the telemedicine group will be educated about the appropriate use of the telemedicine system components. They will be asked to use their CGMs for ongoing automatic glucose monitoring, SIPs for insulin administration with recording insulin use, software applications, and VVC, SM, and telephone for telemedicine visits. Participants in the SoC will receive diabetes education as per standard of care (i.e., frequency of POC checking and proper insulin administration, among others). They will be asked to use POC for glucose monitoring and traditional insulin pens for insulin administration, and they will be asked to document POC, and insulin use as per standard of care.

Then, following the initial baseline visit, patients in the Telemedicine group will have the following interventions:

- i) in-person (Initial) Clinic Visit (Day 0):*

“Improving Glycemic Control in DM2 Patients in the Ambulatory Setting”

PI [name]
NCT04800471

This will be a typical in-person clinic visit. Vital signs, medications, and a medical history will be obtained. POC values will be reviewed, and DM medication adjustments will be performed. CBC, BMP, HbA1c, and urine creatinine/microalbumin will be obtained per usual care.

ii) Telemedicine visits (~every three weeks until +180 days [end of RCT]):

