Approximately every three weeks, patients will have remote visits using the DAT clinic. HCPs obtained CGM and SIP data using software applications (as above). Trends of hyperglycemia and hypoglycemia and their relationship with insulin administration will be identified, leading to adjustments of diabetes medications (insulin or non-insulin). Communication will be done by VVC, SM, or by phone. Patients will be evaluated more (i.e., if acute changes are needed after hypoglycemic events) or less frequently (i.e. if no changes on medications are needed). At the last remote visit (+180 days), all patients will have repeat lab work of CBC, BMP, HbA1c, and urine creatinine/ microalbumin.

iii) Consultation (telecommunication) by an exercise physiologist (Days 0, +90 days, +180 days [end of RCT]):

On day 0, the exercise physiologist will evaluate baseline PA data and medical history, telecommunicate with each participant regarding their PA goals, facilitators, and barriers, and will write a PA prescription (frequency/intensity/duration/type) following best practices 64. On days +90 and +180, he will discuss progress, set motivational intermediate goals to reach the long-term PA prescription objectives, and will modify exercises as needed.

"Improving Glycemic Control in DM2 Patients in the Ambulatory Setting"

PI [name]
NCT04800471

iv) Research Visit: At +180 days (end of RCT):

Subjects will be placed on a "blinded" CGM. After ten days, Veterans will be asked to return the CGM, which will be downloaded. Subjects will complete the Senior Fitness test for PA evaluation.

Following the initial baseline visit, subjects in the SoC group will have the following interventions:

i) One in-person (Initial) Clinic Visit (Day 0):

This visit will be identical to the in-person visit that subjects will be randomized to the Telemedicine group had on Day 0.

ii) Two in-person Clinic Visits (Day +90, +180):

Subjects will have a typical clinic in-person visit. Vital signs and HbA1c will be obtained, physical examinations will be performed, and POC values (either by report, logbook, or glucometer) will be reviewed. Information regarding insulin use and adherence will be obtained through patient reporting. DM medication adjustments will be performed, and patients will be instructed to increase their PA as clinically indicated.

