iii) One Research Visit: This visit will be at +180 days (end of RCT) and will be identical to the research visit of the Telemedicine clinic group.

“Improving Glycemic Control in DM2 Patients in the Ambulatory Setting”

PI [name]
NCT04800471

Outcome Measures

The purpose of this trial will be to examine the feasibility of the above interventions (CGMs, SIPs, Telecommunication systems and promoting PA by EP) combined as a single telemedicine intervention and examine whether it can lead to improvement in hyperglycemia, as defined by a decrease in HbA1c (primary outcome). Secondary outcomes will be time in range (TIR) 70-180 mg/dL, time below range (TBR) <70 mg/dL, TBR <54 mg/dL, time above range (TAR \geq 180 mg/dL and TAR \geq 250 mg/dL. In addition, we will evaluate differences in hypoglycemic events (CGM glucose <70 mg/dL for at least 15 minutes), clinically significant hypoglycemic episodes (CGM glucose < 54 mg/dL for at least 15 minutes), and nocturnal hypoglycemia. For glucose variability, we will evaluate if there is a difference in the Coefficient of Variation (CV).

STATISTICAL ANALYSIS

Student's t-test will be used to compare baseline characteristics of the two groups. For continuous outcome measures (e.g., HbA1c, time <54 mg/dL, etc.), we will use linear regression analyses (SAS proc genmod with a normal distribution and identity link). For outcome measures that will be counts (e.g., number of hypoglycemic episodes <54 mg/dL), we will use Poisson regression (SAS proc genmod with a Poisson distribution and a log link). Regardless of the type of regression we will use, the model will be change in outcome= baseline value + group + time + group + time where group will be control or telemedicine and time will be baseline, three-month, or six-month. We will calculate estimated values at each time point using the mean value of the outcome at baseline, baseline value, (SAS LSMeans statement with a pdiff option). Comparisons of baseline

“Improving Glycemic Control in DM2 Patients in the Ambulatory Setting”

PI [name]
NCT04800471

characteristics will be performed using Student's t-test. A two-tailed $P \leq 0.05$ will indicate significance.

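### Hypoglycemic episode counts are modelled without an offset for recorded CGM time and are not tied to the blinded ten-day wears, so any difference in recorded time between arms enters the count ratio

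*Combined protocol and SAP*

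**What the plan says.** The Statistical Analysis section assigns count outcomes to Poisson regression: "For outcome measures that will be counts (e.g., number of hypoglycemic episodes <54 mg/dL), we will use Poisson regression", implemented as "SAS proc genmod with a Poisson distribution and a log link". One linear predictor serves every outcome type: "the model will be change in outcome= baseline value + group + time + group + time", where "time will be baseline, three-month, or six-month". No offset, rate per unit time, minimum wear or rule for partial sensor data appears there or elsewhere.

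Two sources of CGM data are described under Patient Population-Study Procedures.

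- **Blinded wears, both arms.** At baseline "they will be placed on a ('blinded') Dexcom G6 CGM device for ten days to obtain baseline CGM glucose data". At the +180-day research visit a second blinded sensor is placed: "After ten days, Veterans will be asked to return the CGM, which will be downloaded". The standard-of-care (SoC) research visit "will be identical to the research visit of the Telemedicine clinic group".
- **Ongoing CGM, telemedicine arm only.** "They will be asked to use their CGMs for ongoing automatic glucose monitoring". SoC patients monitor by fingerstick.

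Outcome Measures defines an episode as CGM glucose below 70 or below 54 mg/dL for at least 15 minutes, and adds nocturnal hypoglycemia. It does not say which recordings the episodes come from.

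**The concern.** A log-link Poisson model with no offset estimates a ratio of expected counts. An expected count is event rate multiplied by recorded time, so the group coefficient estimates the rate ratio only when recorded time is the same in both arms. The plan neither adjusts for recorded time nor fixes it to be equal in the analysis.

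Recorded time could differ in two ways. First, ten days is the scheduled wear. A sensor that fails, detaches or comes back early records less, and its lower count would be read as less hypoglycemia. With 15 patients per arm, a few short wears can shift an arm's mean. Second, the model has a three-month level, but no blinded wear is scheduled then in either arm. The only CGM data at that point are the telemedicine arm's own recordings. An analyst must use those for one arm or leave the level empty, and the plan does not say which.

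At stake is the comparison of hypoglycemia under a programme that reviews and adjusts insulin more often than usual care. Recorded time alone could create or mask a difference.

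**Working it through.** The plan has no calculation to reproduce: it states that none was done and that 30 is a convenience sample. The following is an illustration.

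**Inputs from the documents.** 30 patients at 1:1, so 30/2 = 15 per arm; two-sided 0.05; scheduled wear of ten days.

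**Assumptions not in the documents.** Episode rate r of 0.1, 0.3 or 0.6 per day, the same in both arms; mean wear w1 and w2 as listed below; Poisson counts; one end-of-trial comparison without the baseline covariate.

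**Formulas, no offset.**

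- Apparent log ratio = ln(w1/w2), although the true log rate ratio is 0.
- SE = sqrt(1/(15·r·w1) + 1/(15·r·w2)).
- With d = ln(w1/w2)/SE, false-positive rate = P(Z > 1.96 − d) + P(Z < −1.96 − d).

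**Worked case, 9.5 vs 7.5 days, r = 0.3.** ln(9.5/7.5) = 0.236. Expected counts are 15 × 0.3 × 9.5 = 42.75 and 15 × 0.3 × 7.5 = 33.75. SE = sqrt(1/42.75 + 1/33.75) = 0.230. d = 0.236/0.230 = 1.03. The two tails are 0.175 + 0.001, about 18%.

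| Mean wear (days) | Apparent ratio | r = 0.1 | r = 0.3 | r = 0.6 |
|---|---|---|---|---|
| 10 vs 10 | 1.00 | 5% | 5% | 5% |
| 9.5 vs 9 | 1.06 | 5% | 6% | 6% |
| 10 vs 9 | 1.11 | 6% | 8% | 11% |
| 9.5 vs 7.5 | 1.27 | 9% | 18% | 31% |
| 9 vs 6 | 1.50 | 16% | 37% | 64% |

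**Check by simulation** (20,000 replicates, no true difference, r = 0.05, 0.1 and 0.3). Without an offset, 10 vs 9 days gave 3.5%, 5.3% and 7.3%; 10 vs 8 days gave 4.2%, 7.7% and 16.5%. The pattern agrees with the formula, somewhat lower where counts are small. With log days worn as offset, Poisson counts gave about 2.5-5.2% in every wear scenario.

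**What the offset does not cure.** Suppose patients differ in their underlying rate, with variance = mean + mean² (negative binomial, dispersion 1, assumed). At ten days and r = 0.3 the mean per patient is 3 and the variance 3 + 9 = 12, four times the Poisson value, so the true SE is twice the Poisson SE. The false-positive rate is then about 2 × P(Z > 1.96/2) = 33%, even at equal wear. The simulation gave 32% at r = 0.3, 15% at 0.1 and 8% at 0.05, with or without the offset.

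**Fit with the stated response.** The plan makes the change in outcome the response for every regression type. A change in episode count can be negative, which a Poisson model cannot take. Adding an offset to the model as printed would therefore not be enough; the response must be the count.

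**The case against.** The strongest reply is that the design already equalises exposure: both arms have the same blinded ten-day wear at baseline and at +180 days, and the ongoing CGM is described as part of the intervention, used to guide treatment. On that reading the counts come from matched windows, and modest differences in wear matter little.

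Much of this stands. A reader might infer from the bare count model that there is no exposure window at all; the two scheduled wears show otherwise. What is missing is the link from those windows to the counts, and an adjustment for time actually recorded. The reply does not account for the three-month level, which has no matched window.

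Several other inferences are tempting but go beyond the documents:

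- *The arms will have unequal wear.* Longer sensor experience in the telemedicine arm makes this plausible, but no wear data are given, and a gap of half a day to a day has a small effect.
- *The counts are the main safety outcome.* HbA1c is primary and the time-in-range measures are secondary; the episode counts follow as additional evaluations. Hypoglycemia is also covered by time below range.
- *A failed sensor would count as zero episodes.* No rule says so. The plan is silent.
- *The time-in-range outcomes already correct for wear.* The plan does not say whether they are percentages of recorded time.
- *An 18-fold ratio (180/10) is to be expected.* That requires comparing all of the telemedicine arm's ongoing data with one SoC wear. The text does not exclude this, but it does not call for it, and matched wears are available.

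**Conclusion.** The point holds in a conditional form. As written, the count model has no term for recorded CGM time and no stated data source, so any difference in recorded time passes directly into the count ratio. Under the assumptions above, the false-positive rate is about 6-11% at 10 vs 9 days and about 9-31% at 9.5 vs 7.5 days; with equal wear there is no bias. Wear and event rates are assumed throughout. Overdispersion, also assumed, can matter more than a modest wear gap, so an offset alone should not be presented as restoring the 5% level. For a 30-patient pilot this is a correction the plan should make; it does not affect the primary HbA1c analysis.

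**What to change.** In the Statistical Analysis section:

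1. Take the episode counts (below 70, below 54 and nocturnal) only from the blinded wears at baseline and +180 days, in both arms.
2. Model the +180 count itself, not its change, with group and the baseline episode rate as covariates and log valid CGM hours as offset (log valid night-time hours for nocturnal events).
3. Treat a wear with no data as missing.
4. Drop the three-month level for CGM counts.
5. Use a negative binomial model or an overdispersion-robust variance.

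The cost is a short rewrite of the count paragraph and an OFFSET= option in proc genmod; recorded hours should be obtainable from the CGM download. No new data collection is needed. The downsides are somewhat wider intervals and no three-month count estimate, for which no matched CGM data exist in any case.

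### Hypoglycemic episode counts are to be tested with Poisson regression and no allowance for overdispersion; standard errors are too small if patients' episode rates differ beyond what baseline and arm explain

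*Combined protocol and SAP*

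**What the plan says.** The Outcome Measures section makes HbA1c primary and the CGM time-in-range measures secondary. It then adds hypoglycemic events below 70 mg/dL, "clinically significant hypoglycemic episodes (CGM glucose < 54 mg/dL for at least 15 minutes"), and nocturnal hypoglycemia. For outcomes that are counts, the STATISTICAL ANALYSIS section says "we will use Poisson regression (SAS proc genmod with a Poisson distribution and a log link") and gives episodes below 54 mg/dL as its example. The criterion is "A two-tailed $P \leq 0.05$ will indicate significance".

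Under Patient Population-Study Procedures, "we used a convenience sample of 30 subjects" are allocated by a "computer-generated random sequence at a 1:1 ratio", and "No sample size calculations are provided due to the pilot nature of this study". A ten-day blinded CGM wear in both arms is described at baseline and at six months. The document gives no expected episode rate, no variance, and no provision for a variance larger than the mean.

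**The concern.** Poisson standard errors are right only if all patients with the same baseline count and arm share one underlying episode rate. Several features of the design make that doubtful. Eligibility is broad: basal-bolus insulin with or without other drugs, and poor control with no stated threshold. Medication is adjusted patient by patient. A single baseline count from ten days is a noisy measure of a patient's rate and cannot absorb all the differences between patients.

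If rates still differ after adjustment, the variance exceeds the mean, and the model in effect treats each episode, rather than each patient, as independent information. With about 15 patients per arm, one or two patients with many episodes could then produce a nominally significant benefit or harm in an intervention that adjusts insulin. Nothing in the plan would detect or correct this.

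**Working it through.** **Inputs from the document.** Two-sided level 0.05; 30 patients, taken as 15 per arm from 1:1 allocation; Poisson model with log link; baseline value as covariate.

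**Assumed, because the document gives no figure.** The episode mean, the between-patient dispersion k, and the residual variance/mean ratio φ. For gamma-Poisson counts with mean μ, the variance is μ + kμ², so the marginal ratio before baseline adjustment is 1 + kμ. For example, μ = 2 and k = 1 give 1 + 2 = 3.

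**Step 1: reproduce the plan's figure.** If the true variance is φ times the mean, the Poisson standard error is too small by a factor √φ, and the Wald test has

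type I error = 2 × [1 − Φ(1.96/√φ)].

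At φ = 1, which the plan assumes, this is 0.050. A simulation with 15 per arm and truly Poisson counts gave 0.035 to 0.053. The plan's level therefore holds under its own assumption, and small numbers alone do not break it.

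**Step 2: the same formula with φ above 1.** At φ = 2, 1.96/1.414 = 1.386, which gives 0.166.

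| Residual φ (assumed) | Type I error |
|---|---|
| 1.25 | 0.080 |
| 1.42 | 0.10 |
| 2 | 0.166 |
| 3 | 0.258 |
| 4.40 | 0.35 |
| 5 | 0.381 |
| 8 | 0.488 |

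**Step 3: simulation with baseline adjustment.** Gamma-Poisson counts, 15 per arm, no group effect, one follow-up count per patient as response, baseline count as covariate (raw or log), mean 1 to 4 episodes, k from 0.25 to 2, correlation of the underlying rates between baseline and follow-up 0 to 0.8, 1,500 trials per cell.

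| Marginal variance/mean ratio | Type I error, plain Poisson |
|---|---|
| 1.25 | 0.051 to 0.077 |
| 1.5 | 0.086 to 0.118 |
| 2 | 0.119 to 0.169 |
| 3 | 0.159 to 0.261 |
| 5 | 0.227 to 0.378 |
| 9 | 0.343 to 0.525 |

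The baseline covariate helps but does not cure the problem. At a marginal ratio of 5, the error is 0.361 to 0.378 when baseline carries no information and still 0.227 to 0.263 at correlation 0.8.

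**Step 4: sparse or mildly dispersed counts.** At correlation 0.5, leaving out trials with an empty arm or a failed fit (at most 94 of 1,500):

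- mean 0.25: 1.7% (k = 0.5) and 2.6% (k = 1)
- mean 0.5: 4.1% (k = 0.25), 5.0% (k = 0.5) and 7.7% (k = 1)
- mean 1: 6.5% (k = 0.25) and 8.9% (k = 0.5)

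A low mean does not protect if dispersion is strong: mean 0.5 with k = 2 gave 10.5% to 12.7% in repeated runs.

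**Step 5: the remedy.** With the variance scaled by the Pearson dispersion and a t reference on 30 − 3 = 27 degrees of freedom, the overdispersed cells of Step 3 gave 3.5% to 6.9%, and truly Poisson counts gave 3.1% to 5.7%. In sparse cells (mean 0.25 to 0.5) the scaled test was conservative, at 1.1% to 3.5%.

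**The case against.** The strongest reply is that the size of the error cannot be derived from the document. That stands. A reader might infer that false differences will be declared some fixed number of times too often, say 2 to 7 times. That range corresponds to φ of about 1.42 to 4.40, which the document neither states nor implies. With few episodes below 54 mg/dL in a ten-day wear there may be no inflation at all; with strong clustering it can exceed sevenfold (0.525/0.05 = 10.5 in the most extreme cell). That counts are overdispersed is itself an assumption, though the plan makes the opposite assumption without a check.

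A reader might also infer that this is the trial's main safety comparison. The document does not say so. Episode counts come after the primary and secondary outcomes, and time below 70 and below 54 mg/dL, which also measure hypoglycemia, are continuous and do not depend on this model. Nor does the document say that nocturnal hypoglycemia will be analysed as a count.

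Finally, the model as written takes change from baseline as the response for every regression type. A change in a count can be negative (28% to 43% of changes in a no-effect simulation), so the Poisson model cannot be fitted as it stands. The error rates above therefore describe a plan in which the follow-up count is the response. This is a separate fault, but repairing it means rewriting the same passage, and the dispersion problem would remain unless it is dealt with then.

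**Conclusion.** The point holds conditionally. The plan commits to a variance equal to the mean for episode counts and has no safeguard. Any residual overdispersion makes its standard errors too small; how far the false-positive rate then exceeds 5% depends on the degree of overdispersion and the number of episodes, neither of which the document gives. The figures of about 10% to 35% rest on the assumed residual ratio of about 1.4 to 4.4, 15 patients per arm and one follow-up count each. They do not include any further understatement from several time points per patient analysed without a repeated-measures term.

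The primary HbA1c analysis and the conduct of the trial are untouched. For non-primary outcomes in a 30-patient pilot, this should be fixed because the remedy is cheap and sound, but it is not critical.

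**What to change.** Replace the count-model sentence in STATISTICAL ANALYSIS with wording such as:

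> The number of episodes at follow-up (not its change) will be analysed with a log-link quasi-Poisson model, with variance scaled by the Pearson dispersion (for example PROC GLIMMIX with random _residual_) and t tests on residual degrees of freedom, adjusted for the baseline count. The rate ratio will be reported with its 95% confidence interval. If one arm has no episodes, the P-value will come from a re-randomisation test on the difference in mean episode count between arms.

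State also whether the baseline count enters raw or on a log scale.

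The cost is a change of SAP wording and one SAS call, with no new data. Confidence intervals will be somewhat wider where counts are overdispersed, and the test is conservative when episodes are sparse. Fixing the rule before the data are seen avoids a later, data-driven choice of variance model.

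### Poisson regression with a log link is specified for the change in hypoglycemia counts, and that change is negative for every patient who improves

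*Combined protocol and SAP*

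**What the plan says.** All the analysis text is in the Statistical Analysis section of the combined protocol and SAP.

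- Which outcomes are counts: "For outcome measures that will be counts (e.g., number of hypoglycemic episodes <54 mg/dL". The Outcome Measures section defines these events, for example "clinically significant hypoglycemic episodes (CGM glucose < 54 mg/dL for at least 15 minutes", with a parallel definition at 70 mg/dL and an item for nocturnal hypoglycemia.
- Distribution for counts: "we will use Poisson regression (SAS proc genmod with a Poisson distribution and a log link".
- Response and terms: "Regardless of the type of regression we will use, the model will be change in outcome= baseline value + group + time". The group and time terms are then repeated, probably where an interaction was meant.
- Levels: "where group will be control or telemedicine and time will be baseline, three-month, or six-month".

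The next sentence plans estimated values at each time point, evaluated at the mean baseline value. Nothing exempts counts from the change-score response, names the follow-up count as the response, or says how negative values are handled.

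The data for these counts come from blinded sensor wear. At the baseline research visit, both arms wear a "Dexcom G6 CGM device for ten days to obtain baseline CGM glucose data". At the end of the trial the telemedicine arm repeats this: "After ten days, Veterans will be asked to return the CGM, which will be downloaded". For standard of care: "This visit will be at +180 days (end of RCT) and will be identical to the research visit". No three-month sensor wear is scheduled for the standard-of-care arm, so six months is the only change both arms can supply.

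**The concern.** A Poisson variable takes the values 0, 1, 2 and so on. A change in count is negative whenever a patient has fewer episodes at six months than at baseline, which is the result the intervention hopes for. The stated likelihood is undefined for those patients.

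Two outcomes are possible, and the plan does not choose between them.

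- The fit stops. The hypoglycemia counts then have no prespecified analysis, and a replacement is chosen after the data have been seen.
- Negative rows are left out. The loss then depends on the outcome and is larger in the arm that improves more, so the estimate no longer describes the groups as randomised.

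The same sentence has a second fault. Change at baseline is 0 for everyone, so a baseline time level has no finite log mean.

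**Working it through.** **Inputs from the documents.** 30 patients randomised 1:1, so 15 per arm; two-sided 0.05; ten-day blinded wear at baseline and at +180 days in both arms. There is no sample size calculation, event rate or expected effect, so the plan has no figure to reproduce.

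**Inputs assumed.** Mean episodes per ten-day wear m = 1 to 6 (lower values where stated). Six-month to baseline rate ratio of 1 (no effect) or 0.5 in the telemedicine arm and 1 in standard of care. Counts are Poisson, or Poisson with gamma between-patient variation.

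**Step 1: support.** For a Poisson mean of 2, the probabilities at -1 and -2 are both 0 and the log-likelihood is minus infinity. One such patient is enough to make the likelihood undefined.

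**Step 2: share of patients with a negative change.** The difference of two independent Poisson counts has a Skellam distribution. With no effect, P(change < 0) = [1 - exp(-2m) I0(2m)] / 2, where I0 is the modified Bessel function. At m = 1, exp(-2) × I0(2) = 0.1353 × 2.2796 = 0.3085, so P = (1 - 0.3085)/2 = 0.346. The halved column uses the same distribution with means m/2 and m. When telemedicine halves episodes, patients retained after dropping negatives = 30 - 15 × (no-effect share + halved share).

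| m | Share negative, no effect | Share negative, halved | Retained of 30 | Power, six-month count | Power, change with negatives dropped |
|---|---|---|---|---|---|
| 1 | 0.346 | 0.470 | 17.8 | 0.33 | 0.10 |
| 2 | 0.396 | 0.606 | 15.0 | 0.56 | 0.16 |
| 4 | 0.428 | 0.730 | 12.6 | 0.88 | 0.24 |
| 6 | 0.442 | 0.800 | 11.4 | 0.97 | 0.26 |

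The power columns are simulated (plain Poisson counts and model, 3,000 trials per setting); repeat runs agreed within 0.02. With gamma variation (shape 1-2), the shares are 28-46% with no effect and 38-75% with halving. Power, using a Pearson scale and t reference, then falls from 0.22-0.66 to 0.04-0.09.

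**Step 3: could the trial escape by chance?** With no effect, P(none of 30 negative) = (1 - P)^30. At m = 1, 0.654^30 is about 3 in a million, and it is smaller at higher means. At m = 0.2 it is 0.7%, and at m = 0.1 it is 7%.

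**Step 4: attempted fits.** A Poisson log-link model of change on baseline and group was tried on 6 scenarios × 300 simulated trials = 1,800 data sets (means 1, 2 and 4; ratio 1 or 0.5; gamma variation with variance 1). It raised an error in 263 to 299 of each 300, and every remaining fit was non-finite. This was done in Python. SAS was not run, so whether it stops or omits rows is left open.

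**Step 5: who is lost if rows are dropped.** In the halving scenarios of step 4, at means 1, 2 and 4, the telemedicine arm loses 38%, 50% and 62% of patients, against 28%, 33% and 38% in standard of care. The between-arm difference in mean change shrinks from -0.49 to -0.33, from -1.00 to -0.58, and from -2.00 to -0.99. The sign is kept.

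**Step 6: baseline as a time level.** In one additive log-link example with the zero baseline rows kept, the time coefficient was 6.6, 11.5 and 21.5 after 5, 10 and 20 iterations, so it diverges.

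**Step 7: the replacement.** On the six-month count, type I error of plain Poisson was 4-5% without overdispersion and 9-32% with the assumed gamma variation. With a Pearson scale and t reference it was 4-6% throughout. Adding 0.25, 0.5 or 1 to the baseline count before taking logs gave type I error of 4-5% and power within 0.03 of each other.

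**The case against.** The best defence is that the model sentence is a drafting slip. It visibly repeats terms, lists baseline as a time level, and is followed by a plan for estimated values at each time point. All of this fits the outcome itself better than its change. The reading is possible, and the failure follows only from the literal one. But the sentence says explicitly that its response applies whatever the type of regression, and the later line concerns reporting. If the raw count was meant, the text still needs the same correction.

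Other points stand in part.

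- **Reach.** The trial is a pilot, and the counts are listed after the named secondary outcomes. This limits the weight of the concern.
- **Low rates.** The power loss depends on the assumed means. At a mean of 0.2, 15-17% of patients are negative and power is about 0.005 with or without dropping; at 0.5 it is 0.12 against 0.04. With rare events there is little power to lose, although the likelihood is still undefined.
- **Direction of bias.** After dropping, the median fitted ratio was 0.37-0.50 against a true rate ratio of 0.50. The first is a ratio of mean non-negative changes and the second a ratio of event rates, so the pair does not establish a bias direction.
- **Baseline rows.** In an additive example, adding 30 zero rows left the group estimate at -2.538 (SE 1.039). The divergence spoils the time term and the baseline estimates, not that comparison.
- **Simpler covariate.** The raw baseline count did as well at means 1 and 2 (power 0.31 and 0.57, against 0.31 and 0.56 for the log form). Under overdispersion at mean 6 the log form did better (0.76 against 0.67).

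**Conclusion.** The concern holds, with high confidence. That the response and the distribution are incompatible follows from the plan's own wording and needs no assumed rate; the rates decide only how many patients are affected. At assumed means of 1 to 6, roughly a third to four fifths of patients have a value the model cannot take, and a 30-patient trial without one is practically impossible. The main cost is an undefined analysis, or lost data and, at these rates, lost power. A reversed comparison is not shown.

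The concern is confined to the hypoglycemia counts. It should be corrected before the data are analysed, because these counts carry a safety comparison in insulin-treated patients and a repair made afterwards would be post hoc. Overdispersion is plausible but not documented, so the inflated type I error of plain Poisson is conditional on it.

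**What to change.** For count outcomes, replace the model sentence with wording such as: *The response is the six-month count, with a log link and with group and log(baseline count + 0.5) as covariates; baseline is not a time level.* Fit this as Poisson with a Pearson scale and a t reference, and give negative binomial regression as a sensitivity analysis. Report the rate ratio with its 95% confidence interval.

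Add log(sensor wear time) as an offset in case wear differs from ten days. If it does, scale the baseline count to the same ten-day period so that both sides of the model are treated alike. With one follow-up count per patient, no repeated-measures term is needed for these outcomes.

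The cost is revised wording and one changed model statement. The six-month counts are already planned in both arms. The downside is wider intervals than unscaled Poisson when counts are overdispersed.
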